Angeles (UCLA) Life Adversities Screener (LADS)⁶¹—that captures trauma experiences not typically asked about in healthcare settings. To the best of our knowledge, this will be the first study to examine how brief treatment of trauma histories can prepare PLWHIV to address concurrent health conditions such as CVD risk, within community-based healthcare contexts that are also being supported to address these health conditions. As noted above, integrated HIV and chronic disease services show promise for better outcomes among PLWHIV who have co-morbid conditions,¹⁴ but to date, the investigators know very little domestically about how to integrate services, how to support guideline-concordant services for co-morbid conditions, and how to ensure that patients are ready to access those services and engage in appropriate care. This proposed study gives us an opportunity to shape and facilitate two complementary pathways to improved CVD care: the patient pathway and the organizational pathway. With blended, REP-guided implementation strategies⁶² supporting both pathways, the investigators contend that CVD outcomes can be improved and CVD-related services can be strengthened and maintained.

Second, to address multiple co-morbidities, the investigators draw on recent implementation science literature that stresses the importance of multifaceted, modular, flexible interventions⁶³⁻⁶⁵ rather than interventions focused on singular conditions and/or interventions that pose fidelity challenges in usual care settings. Our intervention, Healing our Minds and Bodies (HHMB), represents an improvement over existing interventions in that HHMB addresses multiple, interrelated conditions; draws on a combination of evidence-based and culturally congruent approaches to trauma, HIV, and CVD risk;⁶⁶ reduces barriers to accessing CVD care for a diverse cohort of patients with complex needs;^{67,68} it is specifically intended for populations most impacted by HIV/AIDS (thus enhancing its relevance to our target population); it is group-based, brief, and tailorable to local context; and it can be facilitated by a trained staff member with minimal prior experience of delivering mental health/CVD interventions. As such, it falls within the concept of a “disruptive innovation,”⁶⁹ with its emphasis on simplicity, accessibility, and potential scalability should positive effectiveness and implementation outcomes be achieved.

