4. BASIC STUDY DESIGN

APPROACH

Overview of Study Design

The goal of the project is to increase both patient and organizational readiness to address trauma and CVD risk among PLWHIV in two healthcare organizations in Los Angeles County. These organizations have indicated their strong interest in being able to meet CVD-related needs of their HIV-positive clients and their capacity to do so, with training and support (see Letters of Support). Using an effectiveness/implementation hybrid research design,¹⁵ this study will investigate: (1) organizational factors associated with implementation outcomes⁷⁶ (adoption, guideline adherence, feasibility, sustainability); and (2) effectiveness of the intervention as delivered to 260 PLWHIV receiving care in the two participating organizations. For purposes of this study, the investigators operationalize “successful implementation”⁷⁶ as a combination of number of individuals served (approximately 130 individuals per agency), a minimum of 12 completed cycles of the five-week intervention, delivery of the intervention with fidelity and documentation of adaptations, and high level of satisfaction with the intervention. The investigators will also study maintenance and evolution of the intervention, i.e., whether the participating organizations continue to offer HHMB and CVD-related services after the active implementation period.

To achieve our implementation aims (Aims 1 & 2), a mixed methods evaluation will be conducted throughout each REP phase, as detailed below. Staff and organizational characteristics will be assessed in Year 1, and engagement and training will be priorities. Following successful training, implementation will commence in both organizations in the first year. After a 26-month implementation phase, maintenance and evolution will be studied for six months, during which time only technical assistance will be provided. For our intervention effectiveness aim (Aim 3), the investigators will use an intra-change within subjects (pre/post change) design.

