5. STUDY POPULATION AND ELIGIBILITY CRITERIA

5.1 Overview

Participants for this study will be patients at the two participating agencies, Oasis Clinic and Northeast Valley Healthcare Corporation. The investigators chose patients already in care in order to focus on providing new services rather than to recruit new patients to the clinics for HIV treatment. The latter new population would have to establish trust before assessing their readiness to be involved in their own health care and HIV treatment. The lack of trust is a factor in non-adherence to medication and to the recommendation of health providers. The investigators are targeting patients who have at least some relationship with health providers, and the investigators seek to enhance that trust.

Participating agencies & staff

Two large healthcare organizations in Los Angeles County have agreed to serve as sites for this study: OASIS Clinic and Northeast Valley Health Corporation (NEVHC), a federally qualified health clinic (FQHC). These agencies are well-established, serving large numbers of vulnerable HIV-positive African Americans and Latinos. Because of the needs that they have observed among their clients, these agencies have expressed

| | Total # clients | % Hispanic/Latino | % African American | % women | % below Federal Poverty Level |
|-------|-----------------|-------------------|--------------------|---------|-------------------------------|
| OASIS | 771 | 34 | 62 | 20 | 92 |
| NEVHC | 787 | 61 | 16 | 19 | 72 |

enthusiasm about enhancing CVD- and trauma-related services. These agencies were identified as having met seven key elements

identified in the literature as important in determining agencies' readiness to implement a new intervention.⁸⁷ These include: (1) a respected local community advocate; (2) strong administrative support; (3) formal organizational commitments and stability; (4) commitment of necessary resources to incorporate the program into existing services; (5) program credibility within the community; (6) adequate facilitators/staff; and (7) potential for the program to be self-sustaining or willing to seek additional funding. In addition, the organizations have adequate space for conducting private assessments and group sessions.

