participation in this study involves a number of risks. Although unlikely, breach of confidentiality regarding HIV serostatus and/or trauma histories may cause participants some level of psychological, social or financial distress. Participant HIV serostatus will be kept strictly confidential and known only to the group in which s/he is participating (as all participants will be HIV-positive). Participants are also likely to experience some distress or embarrassment when responding to some of the questions in the assessment, although this is minimized considerably by using the ACASI methodology, which allows participants to respond to sensitive questions in complete privacy. Participants are also likely to feel some discomfort divulging personal information in the group sessions, especially initially. However, the groups will be led by trained facilitators/navigators who will be sensitive to helping participants to moderate this discomfort.

Potential Benefits of Participation

The potential benefits to agency staff who participate in the study are substantial. The agency staff who participates in the training will gain invaluable information and skills that can be utilized in other areas of their careers. The agency's capacity to properly implement this intervention at their agency will be increased. They will also gain capacity to address CVD risk among their HIV-positive clients. Client participants are likely to gain information and skills that can help them live healthier and more fulfilling lives. They may also increase their support networks by meeting others who may have similar CVD risks and/or trauma histories, are affected and infected by HIV, or have other life challenges. In addition, there are several potential benefits of this research to the field and to society with the generation of evidence about the effectiveness of a feasible, flexible intervention targeting multiple co-occurring conditions, as well as evidence about implementation strategies that can support agencies in enhancing their services to address co-morbid health issues.

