Specific Aim 3. To evaluate the clinical outcomes (e.g., improvement on a CVD risk factor or on the 5- or 7-item score) and the effects of the intervention, systematic data analysis and statistical modeling will be carried out: (1) For univariate analysis, the marginal distribution of each measure obtained will be calculated at each time point and across time. For categorical variables (e.g., gender, and race/ethnicity), the frequency distribution and modes will be calculated. For continuous measures (e.g., blood sugar levels/HbA1c), the investigators will calculate the central location (mean and median), variation (standard deviation, kurtosis, etc.), percentiles and range. Statistical tests (e.g., Shapiro-Wilk test) will be used to assess normality of the outcomes. The investigators will evaluate the degree and patterns of missingness, and perform imputation (e.g., multiple imputation), if needed. (2) Bivariate analyses of each outcome measure and independent variables will be carried out. Pearson and Spearman rank correlation will be used to correlate predictors with outcome measures. T-test, analysis of variance (ANOVA) or marginal regressions will be used for continuous measures. The change (delta) of outcome measures between timepoints will be calculated, and distributions of the deltas will be carefully examined. The bivariate analyses between the deltas and covariates will be carried out. Marginal repeated measures models (see model structure below in (3)) will be carried out between each independent measure and outcomes over time. (3) Multivariate repeated measures modeling^{112,113}: To evaluate the relationships between outcome measures and independent variables over time, generalized linear mixed effect models (GLMEM) will be fitted $Y_i = X_i\alpha + Z_i\gamma_i + \varepsilon_i$, controlling for age and others factors. Graphical analyses (e.g., parallel plots) will be used to assist in examining the relationship between predictors and outcome measures over time. Potential non-linear relationships between the outcome measures and the continuous predictors will be explored through generalized additive mixed models.

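### HHMB is delivered in groups, but the Aim 3 analysis specifies no group or agency level, so intervals for mean pre/post change are too narrow if changes within a group are positively correlated

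*Combined protocol and SAP*

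**What the plan says.** The Innovation part of section 3 describes HHMB by saying "it is group-based, brief, and tailorable to local context". Section 13.5 confirms that each client belongs to a particular group: HIV serostatus will be "known only to the group in which s/he is participating". Section 4 counts "a minimum of 12 completed cycles of the five-week intervention" as part of successful implementation, without saying whether that is per agency or in total. The fidelity text in sections 8 and 9 and the Aim 2 text in section 14.1 refer to cohorts.

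For the effectiveness aim, section 4 states: "For our intervention effectiveness aim (Aim 3), the investigators will use an intra-change within subjects (pre/post change) design". Under Specific Aim 3, section 14.1 lists t-tests, ANOVA or marginal regressions, participant-level changes between time points, marginal repeated-measures models and a mixed model: "To evaluate the relationships between outcome measures and independent variables over time, generalized linear mixed effect models (GLMEM) will be fitted". The model equation has one index, i, which is not defined, and the content of Z_i is not given. The adjustment is for age plus further factors that are not named. No group, cycle, cohort or agency term appears. Cohorts and organizations are compared only under Aim 2, for satisfaction ratings.

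**The concern.** Members of one group share the group process and the calendar period, so their changes may resemble each other more than those of people in different groups. A model whose only random effects belong to the participant allows for correlation within a person and treats people as independent.

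Aim 3 has a single arm, so mean change and its interval are the core result. If group-level correlation is ignored, the mean is still estimated without bias, but its standard error is too small and a test of no change rejects too often. Because the number of groups is not stated, the plan does not show how large this could be.

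**Working it through.** **Inputs from the documents.** N = 260, about 130 at each of two agencies (section 4); three assessments: pre, post and 3-month follow-up (client-level data collection, sections 8 and 9); at least 12 five-week cycles; and "After a 26-month implementation phase, maintenance and evolution will be studied for six months". The plan has no figure of its own to reproduce, because it contains no power calculation.

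**Assumptions.** Two-sided 5%, equal groups, no dropout, ICC of change from 0 to 0.10.

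**Number of groups, k.**
- 12: the stated minimum read as a total, one group per cycle.
- 24: 12 cycles at each of two agencies.
- 44: back-to-back cycles, one group at a time per agency; 26 × 30.4 / 35 = 22.6, so 22 complete cycles per agency. Parallel groups are not excluded, so 44 is not an upper bound.

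**Formulas.** m = 260/k; design effect DE = 1 + (m − 1) × ICC; width ratio = √DE; type I error = 2 × [1 − Φ(1.96/√DE)].

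Example, k = 24 and ICC 0.05: m = 10.83; DE = 1 + 9.83 × 0.05 = 1.492; √1.492 = 1.22; error = 2 × [1 − Φ(1.605)] = 10.9%.

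| Groups (m) | ICC 0 | 0.01 | 0.02 | 0.05 | 0.10 | Width ratio at 0.05 |
|---|---|---|---|---|---|---|
| 44 (5.9) | 5% | 5.6% | 6.1% | 7.9% | 10.8% | 1.12 |
| 24 (10.8) | 5% | 6.1% | 7.3% | 10.9% | 16.4% | 1.22 |
| 12 (21.7) | 5% | 7.4% | 9.9% | 16.9% | 26.3% | 1.43 |

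**Check by simulation.** A participant-random-intercept model with three time points and agency-by-time as a fixed effect (10,000 trials per scenario) gave 7.7 / 10.8 / 17.6% at ICC 0.05 with 44 / 24 / 12 groups. An agency term alone therefore does not remove the problem.

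**Which remedy works.**
1. *Group intercept constant over time.* It enters the pre and post values equally and cancels from their difference. In simulation (24 groups, ICC 0.05) the standard error of change was 0.0613 with and without it, against a correct value of √(1.492/260) = 0.0757.
2. *One exchangeable group-by-time variance over three assessments.* Suppose a group effect b appears at post and persists. Deviations from the group's own mean are −2b/3, b/3 and b/3. Their sum of squares is 2b²/3 on 2 degrees of freedom, so the fitted variance is about b²/3. The implied variance of the pre-to-post difference is 2b²/3, two-thirds of the true b². With 12 groups at ICC 0.05 the modelled design effect is 0.95 + 21.67 × 0.05 × 2/3 = 1.672 against a true 2.033, giving an error of 2 × [1 − Φ(1.96/√(2.033/1.672))] = 7.5%. Simulation gave 7.3 / 6.3 / 6.0% at ICC 0.05 and 8.8 / 7.3 / 6.7% at ICC 0.10 with 12 / 24 / 44 groups.
3. *Changes analysed by group.* A group-level analysis of pre-to-post changes held 4.8–5.3%. Group-clustered standard errors with a small-sample correction gave 4.6–5.3% with equal groups, and 4.7–6.2% with unequal groups (coefficient of variation of size about 0.4, assumed), highest with 12 groups.

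**The case against.** **The models could carry a group term.** This stands as far as it goes. The mixed-model equation is generic, marginal models can use clustered errors, and agency might be among the unnamed adjustment factors. A reader might infer that the plan excludes clustering; the text does not support that. It leaves the level unspecified, and the t-tests and change scores are given no such provision.

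**The size is unknown and may be small.** This also stands. The larger figures need an ICC of 0.05 or more with few groups. The 12-cycle minimum belongs to a definition of success; it does not guarantee a number of groups. A reader should not take 17% or 26% as expected error rates.

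**A shared facilitator gives little support for a group-level correlation.** Correct. Section 15.1 provides one facilitator per agency, with the Project Coordinator also trained, so a facilitator effect is mostly an agency effect. The case rests on shared group process and calendar time.

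**Fidelity associations.** The qualitative analysis text in section 14.1 plans statistical associations of fidelity and other process variables with outcomes, and names no unit of analysis. A reader might infer that these will be anti-conservative. That holds only if they are tested on individuals and outcomes are positively correlated within groups, and no test is stated. Nor do the 15% of later recordings that are scored limit the analysis to those groups, because facilitators also complete adherence surveys.

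**Attribution matters more than precision in a single-arm design, and Aim 3 states no alpha or hypothesis.** True, and this limits the weight of the point. Mean change will still be reported with an interval, and that interval should be right.

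**Conclusion.** The point holds in conditional form. Delivery is by group, and no Aim 3 analysis specifies a group or agency level. If changes are positively correlated within groups, a participant-only analysis overstates the precision of mean change, moderately at an ICC of 0.05 and little at 0.01 to 0.02 with 24 or more groups. With no correlation there is no error.

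These sizes rest on an assumed ICC, alpha and number of groups, equal group sizes and complete continuous data. Non-Gaussian outcomes were not simulated. A reader might infer that the estimated change is biased, or that clustering would help attribute it to HHMB; neither follows, since only the standard error is affected. The omission is worth correcting because it is cheap to put right and two natural later repairs, a constant group intercept and a single group-by-time variance, do not fully work.

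**What to change.** In Specific Aim 3 of section 14.1:

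1. Define i as the participant, and carry an intervention-group identifier (cycle within agency, and parallel group if any) into the dataset.
2. State: *Inference on each change from baseline (pre to post, pre to 3 months) is clustered by intervention group, using participant changes with group-clustered standard errors and a small-sample correction, or an equivalent group-level analysis, with degrees of freedom based on the number of groups; agency is a fixed effect.*
3. Do not rely on a time-constant group intercept, and do not make a single exchangeable group-by-time variance the primary method.
4. For non-Gaussian outcomes such as smoking, use the planned marginal models with group-clustered, small-sample-corrected errors.
5. For the fidelity–outcome associations, treat group as the clustering unit, without restricting the analysis to groups that have a scored recording.

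**Cost.** Analysis wording and one identifier, which the planned attendance monitoring should be able to supply. Intervals widen slightly even at ICC 0, because the t critical value then has groups minus 2 degrees of freedom: 2.018, 2.074 and 2.228 with 44, 24 and 12 groups against 1.969 on 258, which is 1.02, 1.05 and 1.13 times as wide. At ICC 0.05 the total widening is 1.14, 1.29 and 1.61 times.

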15.2. DSMB

The DSMB, comprised of CV, diabetes, trauma, and HIV experts as well as a community member, will be convened to oversee the conduct of this study and to monitor patient safety. The DSMB will meet twice a year, at which time the investigators will present data on enrollment, retention, and implementation progress. The DSMB will be responsible for reviewing with the project team the provided data, determine the safety of continuing the study, and will be given the authority to bring the study to a close if they deem it necessary. The PIs and biostatistician will provide to the DSMB any additional information on request. Materials will be circulated at the meetings and minutes will be maintained.

16. ETHICS AND GOOD CLINICAL PRACTICE

All investigators and project staff directly involved with participants will be required to maintain current, required CITI certification and any other ethics and good clinical practice compliance certifications.

18. APPENDICES

[Appendices of measures will be supplied when programmed, IRB-approved versions are available.]
